4.4 Blinding

This section is not applicable as this is an open-label study.

4.5 Assignment and Allocation

Randomization in a 1:1 ratio to each of the 2 treatment arms will be performed via Interactive Response Technology (IRT). Randomization will be stratified by ECOG PS (0, 1 or 2), EGFR mutation type (exon 19 deletion or mutation in exon 21 L858R), TKI chosen (erlotinib versus gefitinib) and race (Asian versus nonAsian). At the beginning of the trial, prior to site initiation and shipment of study drug supplies, each investigator will select either erlotinib or gefitinib to be utilized for all patients randomized to the comparator arm at their site. Prior to

the initiation of the study treatment, the site staff will contact the IRT in order to determine the randomly assigned treatment arm. Specific procedures for randomization through the IRT are contained in the study procedures manual.

5 TREATMENTS AND EVALUATION

5.1 Dosing and Administration of Study Drug(s) and Other Medication(s)

5.1.1 Dose/Dose Regimen and Administration Period

ASP8273 300 mg and erlotinib 150 mg will be taken orally once daily, on an empty stomach defined as no food for at least 2 hours before and 1 hour after dosing, at approximately the same time(s) every day.

Gefitinib 250 mg will be taken orally once daily, with or without food, at approximately the same time every day.

Concomitant medications should not be administered within 2 hours before or after dosing with ASP8273, erlotinib or gefitinib.

If a study drug dose is missed, it should be taken as soon as the subject remembers unless more than 12 hours has passed since the intended dosing time, in which case the subject should wait and take the next scheduled dose. Subjects should not make up a missed dose by taking a double dose at the next scheduled dose.

5.1.2 Increase or Reduction in Dose of the Study Drug(s)

Dosing for ASP8273, erlotinib or gefitinib may be interrupted for any event if the investigator deems it necessary to ensure subject safety. Dosing for ASP8273 or erlotinib may be reduced if necessary. Subjects requiring a treatment interruption should be re-evaluated not longer than 7 days from initial interruption and restarted on study drug as soon as clinically stable. The subject may be discontinued from treatment if there is an interruption of treatment for > 14 consecutive days despite optimal treatment of side effects. A discussion with the Medical Monitor should occur to confirm if the subject should continue on study treatment.

In the event of acute onset or worsening of pulmonary symptoms likely suggestive of ILD (dyspnea, cough, fever), study drug should be interrupted and a prompt investigation of these symptoms should occur and appropriate treatment initiated. If ILD is confirmed, study drug should be discontinued, and the subject should be treated appropriately per local standard of care.

Study drug should be interrupted if the subject experiences eye toxicity such as acute and severe eye pain or keratitis. Subjects with suspected keratitis should have study drug withheld until recovery and discontinued for persistent severe keratitis. Subjects with ocular toxicities should be evaluated by an ophthalmologist.

If the subject experiences severe hepatic impairment, study drug should be discontinued and the subject should be treated appropriately per local standard of care.

5.1.2.1 ASP8273 Dose Modification

Subjects requiring a dose reduction may be re-escalated one dose level (i.e., subjects reduced to 100 mg may only be re-escalated to 200 mg). If the event leading to the reduction recurs, the subject should be reduced to the lower dose level and not re-escalated again. If a grade 3 or 4 study drug-related toxicity persists, or recurs after 2 dose reductions, the subject will be permanently discontinued from ASP8273 treatment. Additionally, if after resolution of a Grade 4 event (except diarrhea, nausea and vomiting) requiring dose interruption and/or dose reduction, the event reoccurs at a G3 or higher the subject should be permanently discontinued from ASP8273.

Table 3 ASP8273 Dose Modification

Dose level	ASP8273 dose (mg qd)
Starting dose	300
-1	200
-2	100

Table 4 Events Requiring ASP8273 Dose Modification

ASP8273 Dose Modification Criteria	
Diarrhea, nausea, vomiting	
Grade 1	
 Continue at same dose
Grade 2	
 Continue at same dose if tolerable and manage as clinically indicated at the discretion of the investigator
Grade 3 or 4	
 Interrupt dosing until the AE is managed to Grade \leq 1 or baseline, then resume treatment at the same dose If the AE recurs at Grade \geq 3 when the same dose is resumed, then interrupt dosing until the AE is managed to Grade \leq 1 or baseline, then resume treatment 1 dose level lower
Neuropathy	
Grade 1	
 Continue at same dose
Grade 2	
 Interrupt dosing at the discretion of the investigator until AE recovers to \leq Grade 1 or baseline and resume treatment at the same dose. Investigate etiology of the neuropathy at the discretion of the investigator If Grade 2 recurs after resuming study drug, reduce treatment to 1 dose level lower
Grade 3	
 Interrupt dosing until the AE recovers to \leq Grade 1 or baseline. Investigate etiology of the neuropathy at the discretion of the investigator Dosing may be resumed, at the discretion of the investigator, 1 dose level lower If Grade \geq 3 recurs after resuming study drug, discontinue study drug permanently
Grade 4	
 Permanently discontinue study drug and manage as clinically indicated at the discretion of the investigator

Table continued on next page

ASP8273 Dose Modification Criteria	
Hyponatremia	
Grade 1	
 • Recheck serum sodium levels as clinically indicated • In addition, urine osmolality, serum osmolality, and urine sodium concentrations should also be measured as clinically indicated • Dosing may continue without interruption at the discretion of the investigator
Grade 2	Not defined by NCI CTCAE v4.3
Grade 3	
 • For serum sodium levels < 130 – 125 mmol/L dosing may continue at the discretion of the investigator with additional monitoring as noted below • For serum sodium levels < 125 mmol/L interrupt dosing • Serum sodium levels, serum osmolality, urine osmolality and urine sodium concentrations should be measured to determine the etiology of the hyponatremia and continue to be drawn as clinically indicated until the serum sodium levels recover \leq Grade 1 or baseline • Consider fluid management plan if clinically indicated at the discretion of the investigator • Dosing should be held until serum sodium levels recover to \leq Grade 1 or baseline, then dosing may resume, at the discretion of the investigator, at 1 dose level lower • If Grade \geq 3 hyponatremia recurs after resuming ASP8273 at a reduced dose, ASP8273 may be discontinued
Grade 4	
 • Interrupt dosing immediately • Consider intravenous infusion of hypertonic saline, fluid management, or other management plan as clinically indicated at the discretion of the investigator • Serum sodium levels, serum osmolality, urine osmolality and urine sodium concentrations should be measured to determine the etiology of the hyponatremia and continue to be drawn as clinically indicated until the serum sodium levels recover \leq Grade 1 or baseline • Correct sodium level at appropriate correction rate to avoid the risk of central pontine myelinolysis • Dosing should be held until serum sodium levels recover to \leq Grade 1 or baseline, then treatment may resume, at the discretion of the investigator, at 1 dose level lower • If Grade \geq 3 hyponatremia recurs after resuming drug at a reduced dose discontinue ASP8273

Table continued on next page

ASP8273 Dose Modification Criteria	
AST or ALT Elevation¹	
Grade 3	
 Interrupt dosing until the AE recovers to grade \leq 1 or baseline, then resume treatment at the same dose level or 1 dose level lower at the discretion of the investigator If Grade \geq 3 AST or ALT elevation recurs after resuming study drug at the same dose level, an additional rechallenge at a reduced dose may be considered, at the discretion of the investigator, once the AE recovers to grade \leq 1 or baseline. If Grade \geq 3 AST or ALT elevation recurs after resuming study drug at a reduced dose, discontinue study drug
Grade 4	
 Interrupt dosing until the AE recovers to grade \leq 1 or baseline At the discretion of the investigator, either discontinue study drug or resume study drug 1 dose level lower If Grade \geq 3 AST or ALT elevation recurs after resuming study drug at a reduced dose, discontinue study drug
Interstitial Lung Disease	
Any grade	
 If ILD is suspected, ASP8273 should be interrupted immediately pending diagnostic evaluation. If ILD is diagnosed, ASP8273 should be discontinued permanently and appropriate treatment instituted as necessary.
Other adverse events, including ocular toxicity	
Grade 3	
 Interrupt dosing until the AE recovers to grade \leq 1 or baseline, then resume treatment at the same dose level or 1 dose level lower at the discretion of the investigator If Grade \geq 3 AE recurs after resuming study drug at the same dose, an additional rechallenge at a reduced dose may be considered, at the discretion of the investigator, once the AE recovers to grade \leq 1 or baseline If Grade \geq 3 AE recurs after resuming study drug at a reduced dose, discontinue study drug
Grade 4	
 Interrupt dosing until the AE recovers to grade \leq 1 or baseline At the discretion of the investigator, either discontinue study drug or resume study drug 1 dose level lower If Grade \geq 3 AE recurs after resuming study drug at a reduced dose, discontinue study drug

¹ Hold ASP8273 and repeat AST and ALT within 1 day to confirm abnormal results before discontinuing subject from ASP8273 treatment.

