1.3 Summary of Key Safety Information for Study Drugs

1.3.1 ASP8273

A total of 170 subjects with NSCLC in ongoing Studies 8273-CL-0101 and 8273-CL-0102 have received at least 1 dose of ASP8273 mesilate, with dose ranging from 25 mg to 600 mg (1 subject received a single dose of 800 mg due to overdose). The majority of subjects experienced at least 1 treatment-emergent adverse event (TEAE). In ongoing Study 8273-CL-0101, the 3 most common TEAEs in both studies were diarrhoea, nausea and vomiting; and in ongoing Study 8273-CL-0102, the 4 most common TEAEs were diarrhoea, nausea, constipation and fatigue.

To date, no subject has died due to an adverse event (AE) in ongoing Study 8273-CL-0101. In ongoing Study 8273-CL-0102, 4 subjects experienced TEAEs leading to death (1 subject each experienced respiratory failure [400 mg group], depressed level of consciousness [100 mg group], progression of NSCLC [200 mg group] and multi-organ failure [200 mg group]; all of which were considered not related to ASP8273 mesilate by the investigator.

To date, in ongoing Study 8273-CL-0101, 23 subjects experienced serious AEs (SAEs). Of these, 13 subjects experienced SAEs that were considered possibly or probably related to

study drug. The only drug-related SAEs occurring in more than 1 subject were nausea (4 events), ALT increased (4 events) and hyponatraemia (2 events). In ongoing Study 8273-CL-0102, 19 subjects experienced SAEs. Of these, 3 subjects experienced SAEs that were considered possibly or probably related to study drug (1 event each of nausea [400 mg group], pancreatitis [300 mg], hyponatremia [500 mg group] and urinary retention [500 mg group]).

To date, 2 subjects from Study 8273-CL-0101 (100 and 600 mg group) and 3 subjects (100, 200 and 400 mg group) from Study 8273-CL-0102 permanently discontinued due to a TEAE (primary reason). Nausea, vomiting and hyponatremia were the only drug-related TEAEs resulting in withdrawal of drug.

In ongoing Study 8273-CL-0101, 9 subjects experienced DLTs (400 mg group, n = 5; 600 mg group, n = 4). Diarrhoea was the most common DLT, occurring in 3 subjects. Nausea and colitis each occurred in 2 subjects, while the rest of the DLTs occurred in 1 subject each. In ongoing Study 8273-CL-0102, 3 subjects in the 400 mg group experienced DLTs; they were diarrhea, anorexia and hyponatremia (2 events in 1 subject).

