12.2 Liver Safety Monitoring and Assessment

Any subject enrolled in a clinical study with active drug therapy and reveals an increase of serum aminotransferases (AT) to $> 3 \times \text{ULN}$ (to $> 5 \times \text{ULN}$ in subjects with liver metastases), or total bilirubin $> 2 \times \text{ULN}$, should undergo detailed testing for liver enzymes (including at least ALT, AST, ALP, and TBL). Testing should be repeated within 48 to 72 hours of notification of the test results. Alerts will be generated by the central lab regarding moderate and severe liver abnormality to inform the investigator, study monitor and study team. Subjects should be asked if they have any symptoms suggestive of hepatobiliary dysfunction.

Definition of Liver Abnormalities

Confirmed abnormalities will be characterized as moderate and severe where ULN:

	ALT or AST		Total Bilirubin
Moderate	$> 3 \times \text{ULN}$ (in patients without liver metastases), $> 5 \times \text{ULN}$ (in patients with liver metastases)	or	$> 2 \times \text{ULN}$
Severe*	$> 3 \times \text{ULN}$	and	$> 2 \times \text{ULN}$

In addition, the subject should be considered to have severe hepatic abnormalities for any of the following:

- ALT or AST $> 8 \times \text{ULN}$
- ALT or AST $> 5 \times \text{ULN}$ for more than 2 weeks (in the absence of liver metastases)
- ALT or AST $> 3 \times \text{ULN}$ and INR > 1.5 (If INR testing is applicable/evaluated).
- ALT or AST $> 3 \times \text{ULN}$ with the appearance of fatigue, nausea, vomiting, right upper quadrant pain or tenderness, fever, rash and/or eosinophilia ($> 5\%$).

The investigator may determine that abnormal liver function results, other than as described above, may qualify as moderate or severe abnormalities and require additional monitoring and follow-up.

Follow-up Procedures

Confirmed moderate and severe abnormalities in hepatic functions should be thoroughly characterized by obtaining appropriate expert consultations, detailed pertinent history, physical examination and laboratory tests. The site should complete the Liver Abnormality Case Report Form (LA-CRF) that has been developed globally and can be activated for any study. Subjects with confirmed abnormal liver function testing should be followed as described below.

Confirmed moderately abnormal LFTs should be repeated 2 to 3 times weekly then weekly or less if abnormalities stabilize or the study drug has been discontinued and the subject is asymptomatic.

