Severe hepatic liver function abnormalities as defined above, in the absence of another etiology may be considered an important medical event and may be reported as an SAE. The

sponsor should be contacted and informed of all subjects for whom severe hepatic liver function abnormalities possibly attributable to study drug are observed.

To further assess abnormal hepatic laboratory findings, the investigator is expected to:

- Obtain a more detailed history of symptoms and prior or concurrent diseases. Symptoms and new onset-diseases should be recorded as 'AEs' on the AE page of eCRF. Illnesses and conditions such as hypotensive events, and decompensated cardiac disease that may lead to secondary liver abnormalities should be noted. Nonalcoholic steatohepatitis (NASH) is seen in obese hyperlipoproteinemic, and/or diabetic patients and may be associated with fluctuating aminotransferase levels. The investigator should ensure that the medical history form captures any illness that predates study enrollment that may be relevant in assessing hepatic function.
- Obtain a history of concomitant drug use (including nonprescription medication, complementary and alternative medications), alcohol use, recreational drug use and special diets. Medications, including dose, should be entered on the concomitant medication page of the eCRF. Information on alcohol, other substance use and diet should be entered on the LA-CRF or an appropriate document.
- Obtain a history of exposure to environmental chemical agents.
- Based on the subject's history, other testing may be appropriate including:
 - acute viral hepatitis (A, B, C, D, E or other infectious agents).
 - ultrasound or other imaging to assess biliary tract disease
 - other laboratory tests including INR, direct bilirubin
- Consider gastroenterology or hepatology consultations.
- Submit results for any additional testing and possible etiology on the LA-CRF or an appropriate document.

Study Discontinuation

In the absence of an explanation for increased LFT's, such as viral hepatitis, preexisting or acute liver disease, presence of liver metastases, or exposure to other agents associated with liver injury, the subject may be discontinued from the study. The investigator may determine that it is not in the subject's best interest to continue study enrollment. Discontinuation of treatment should be considered if:

- ALT or AST $> 8 \times$ ULN

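### No explicit ASP8273 rule ties ALT or AST > 3 x ULN with total bilirubin > 2 x ULN to a mandatory hold or a bar on rechallenge, and Table 4 allows same-dose restart after Grade 3 AST/ALT whatever the bilirubin was

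*Protocol*

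**What the plan says.** **Dosing rules for ASP8273.** Protocol Section 5.1.2.1, Table 4, has AST/ALT rows for Grade 3 and Grade 4. Both order an interruption until recovery to Grade 1 or baseline. After Grade 3 the instruction is "then resume treatment at the same dose level or 1 dose level lower at the discretion of the investigator". After Grade 4 the investigator either stops the drug or resumes one level lower. Neither row refers to bilirubin, and Table 4 has no bilirubin row and no combined row. Its footnote to the AST/ALT heading says "Hold ASP8273 and repeat AST and ALT within 1 day to confirm abnormal results before discontinuing subject from ASP8273 treatment". For suspected lung toxicity the same table is firmer: "If ILD is suspected, ASP8273 should be interrupted immediately pending diagnostic evaluation".

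**General rules.** Section 5.1.2 says that any study drug "may be interrupted for any event if the investigator deems it necessary to ensure subject safety". It also says "If the subject experiences severe hepatic impairment, study drug should be discontinued". The synopsis repeats the second rule. Severe hepatic impairment is given no laboratory definition.

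**Liver appendix.** Appendix 12.2 classes ALT or AST > 3 x ULN together with total bilirubin > 2 x ULN as severe, and its footnote ties this to Hy's law. On monitoring it says "Testing should be repeated within 48 to 72 hours of notification of the test results". On stopping, a list that includes this pattern opens with "Discontinuation of treatment should be considered if". A separate line in the list uses > 5 x ULN with the same bilirubin limit for patients with liver metastases. A firm stop is stated only where close monitoring is not possible.

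**Comparators.** Bilirubin enters the interruption rules for both: erlotinib in Section 5.1.2.2, and gefitinib in the Section 5.1.2.3 table, at Grade 2 or above.

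**The concern.** Appendix 12.2 treats the combined pattern as a serious warning. Its footnote gives 10% to 50% mortality or transplant for drug-induced jaundice of hepatocellular origin. The document that tells sites how to dose, Table 4, does not recognise the pattern. A site following the Grade 3 row exactly may therefore restart the investigational drug at full dose after a Hy's-law picture, and two investigators with identical results could act differently without either departing from the protocol.

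Raised ALT is not a remote possibility with this drug. Section 1.3.1 reports four drug-related serious events of ALT increased in Study 8273-CL-0101, one of only three drug-related SAE terms seen there in more than one subject. SAP Section 7.5.2.1 already plans to count subjects with ALT and/or AST > 3 x ULN and bilirubin at or above 2 x ULN in the same sample. The sponsor thus expects to report the pattern, but gives sites no firm dosing instruction for it.

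**Working it through.** The plan gives no figure to reproduce. The check is to run the combined pattern (ALT or AST > 3 x ULN, total bilirubin > 2 x ULN) through every rule that could apply to ASP8273.

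| Case | Hold required by Table 4? | Restart rule | Bilirubin condition on restart |
|---|---|---|---|
| A. AST/ALT Grade 3 | Yes | Same dose or one level lower | None |
| B. AST/ALT Grade 4 | Yes | Stop, or one level lower | None |
| C. AST/ALT below Grade 3, bilirubin itself Grade 3 or 4 | Yes, under the row for other adverse events | Grade 3: same dose or one level lower; Grade 4: stop, or one level lower | None specific to the combination |
| D. AST/ALT below Grade 3, bilirubin > 2 x ULN but below Grade 3 | No row applies | Not addressed | Not addressed |

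**Restart gap (case A).** This needs no assumption about CTCAE limits. The hold is mandatory, but once ALT recovers the row allows 300 mg again in a subject who was on the starting dose, whatever the bilirubin had been. Case B excludes the same dose but still does not bar rechallenge.

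**Hold gap (case D).** This exists only if Grade 3 starts above 3 x ULN. The documents cite CTCAE version 4.03 (Section 5.5.4) but do not print its limits.
- If Grade 3 starts at 5 x ULN (assumption), case D covers AST/ALT from 3 to 5 x ULN.
- If Grade 3 started at 3 x ULN, case D would be empty and only the restart gap would remain.

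Where case D exists, four rules could stop dosing:
- the general permission to interrupt, which is discretionary;
- the Appendix 12.2 list, which asks only for consideration;
- the severe hepatic impairment rule, which is firm but undefined and not linked to the Appendix 12.2 severe class;
- the rule on monitoring not being possible, which is firm but conditional.

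The Table 4 footnote does not close the gap. It orders a hold as a step before discontinuing, and its repeat covers AST and ALT but not bilirubin.

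**Exposure in case D.** At 300 mg once daily, if the investigator does not hold while awaiting the Appendix 12.2 repeat:
- 48 hours: 2 doses, 2 x 300 = 600 mg;
- 72 hours: 3 doses, 3 x 300 = 900 mg.

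If the investigator holds, the figure is 0. An immediate-hold rule makes it 0 for everyone.

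**Number of subjects.** This cannot be derived. Section 1.3.1 gives four serious ALT events, with 170 subjects treated across two studies at 25 to 600 mg. It does not give the grade of those events or the bilirubin values. It contains nothing on sub-Grade 3 ALT with raised bilirubin, which is what case D would need.

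**The case against.** The strongest reply is that the plan already guards this pattern. Table 4 orders a hold for every Grade 3 or 4 AST/ALT elevation. Sections 5.4.2.1 and 5.5.6 send hepatic adverse events to Appendix 12.2, so Table 4 is not read alone. The central laboratory alerts the investigator, the monitor and the study team, and the sponsor is to be told of severe cases possibly due to study drug. An investigator weighing discontinuation under Appendix 12.2 is pointed by the Table 4 footnote to a hold and a 1-day repeat. Graded discretion was also deliberate: the Amendment 1 rationale wants interruptions kept short because of disease progression after interruption in the early studies.

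Most of this stands, and it rules out two stronger readings that a reader might reach.
- **That no rule requires ASP8273 to be held when this pattern occurs, so that dosing rests on discretion alone.** Table 4 contradicts this for Grade 3 and 4 AST/ALT. Section 5.1.2 adds a discontinuation rule for severe hepatic impairment, and Appendix 12.2 adds one where close monitoring is not possible.
- **That a rate per 300 ASP8273 subjects can be given.** Any rate would rest on an unsourced fraction with raised bilirubin, applied to serious ALT events of unknown grade. Those that were Grade 3 or 4 would already be held.

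The comparator contrast has a limit too. The gefitinib and erlotinib sections support using bilirubin to trigger a hold, but neither writes a bar on rechallenge specific to the combined pattern.

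The reply does not reach the restart. No safeguard listed prevents a same-dose restart after Grade 3 ALT with raised bilirubin, and none defines when severe hepatic impairment has occurred.

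**Conclusion.** The point holds in a limited form. No explicit ASP8273 rule links the Appendix 12.2 severe pattern to a mandatory hold or a bar on rechallenge, and Table 4 and that appendix do not refer to each other. The same-dose restart after Grade 3 follows from the text without assumptions. The missing hold below Grade 3 depends on Grade 3 starting above 3 x ULN. The number of subjects affected is unknown, and no number of outcomes prevented is claimed. The case rests on the severity of the pattern and the clarity of the instruction, not on frequency. It is a patient-safety improvement that the sponsor should make.

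**What to change.** Add one row to Table 4 with this content:
- **Trigger:** ALT or AST > 3 x ULN (> 5 x ULN in subjects with liver metastases, as in the Appendix 12.2 discontinuation list) with total bilirubin > 2 x ULN. For documented Gilbert's syndrome, require instead a clear bilirubin rise above the subject's own baseline.
- **Action:** interrupt ASP8273 at once; repeat ALT, AST, ALP and bilirubin (total and direct) within 1 day; follow Appendix 12.2.
- **Confirmed, no other cause found:** discontinue permanently.
- **Another cause found:** resume only after recovery to Grade 1 or lower, or baseline, under the existing AST/ALT rows. For an elevation below Grade 3, say that the Grade 3 row applies.

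State in Section 5.1.2 that this pattern, without another cause, counts as severe hepatic impairment. Leave the rules for isolated AST/ALT elevation unchanged.

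The cost is one row and one sentence in an amendment. All the tests are already in the Appendix 12.11 biochemistry panel. The 5 x ULN trigger matters because inclusion criterion 12 admits subjects with liver metastases at AST/ALT up to 5 x ULN; a 3 x ULN trigger could hold some of them for a bilirubin rise alone. The Gilbert's allowance belongs on the hold as well as the restart, because those subjects are exempt from the entry limit on bilirubin.

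The downside is a small, unquantified number of extra holds. Some will outlast 1 day while viral, imaging or specialist work-up is done, and some will fall on subjects whose bilirubin rise is due to disease.

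### For recurrent Grade 3 AST/ALT elevation, neuropathy and other adverse events, Table 4 stops ASP8273 where the Section 5.1.2.1 text provides for a lower dose, and neither is said to govern

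*Protocol*

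**What the plan says.** Protocol Section 5.1.2.1 opens with general text and then gives Tables 3 and 4. Table 3 lists a 300 mg start, 200 mg (level -1) and 100 mg (level -2).

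The text has a re-escalation allowance ("subjects reduced to 100 mg may only be re-escalated to 200 mg") followed by three rules:

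- **Rule A, recurrence of the event:** "If the event leading to the reduction recurs, the subject should be reduced to the lower dose level and not re-escalated again".
- **Rule B, discontinuation:** "If a grade 3 or 4 study drug-related toxicity persists, or recurs after 2 dose reductions, the subject will be permanently discontinued".
- **Rule C, Grade 4 events:** "if after resolution of a Grade 4 event (except diarrhea, nausea and vomiting) requiring dose interruption and/or dose reduction", then "the event reoccurs at a G3 or higher the subject should be permanently discontinued from ASP8273".

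Table 4 sets actions by event and grade:

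- **Other adverse events, including ocular toxicity (Grade 3 and Grade 4 rows):** if a Grade 3 or higher "AE recurs after resuming study drug at a reduced dose, discontinue study drug".
- **AST/ALT elevation (Grade 3 and Grade 4 rows):** the same instruction.
- **Neuropathy, Grade 3:** drug may be resumed one level lower. Any Grade 3 or higher recurrence after resuming means permanent discontinuation, with no reference to the dose at which it recurs.
- **Hyponatremia:** after recurrence at a reduced dose, discontinuation is optional if the first event was Grade 3 and required if it was Grade 4.
- **Diarrhea, nausea and vomiting, Grade 3 or 4:** after recurrence at the same dose, interrupt, "then resume treatment 1 dose level lower". There is no discontinuation line.

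The synopsis repeats the three text rules with small differences and refers to Section 5.1.2 for detail.

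**The concern.** Text and table sit in the same section and are addressed to the same investigator. For a Grade 3 event that returns after a reduction, one passage points to a lower dose and the other to stopping. ASP8273 has no precedence sentence. The erlotinib section, by contrast, expressly allows a second reduction to level -2 on recurrence and says the local label should be followed.

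What is at stake is first the consistent handling of a safety event, and then the data that depend on it. A subject continued at a lower level complies with the text but, under Table 4, could be classed as PD2 (met withdrawal criteria, not withdrawn) or PD3 (incorrect dose) in Protocol Sections 7.8 and 8.1.6. More than 14 days on a dose the protocol does not permit may exclude a subject from the PPS (SAP Section 5.2.1), the set used to judge robustness. Time on drug and relative dose intensity (SAP Section 7.3.2) would also vary by site. The ambiguity exists in Arm A only, in an open-label trial.

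**Working it through.** No arithmetic beyond a count applies. The check follows one subject through both passages: a first event, a reduction to 200 mg, then recurrence of the same event at Grade 3 or higher while still on 200 mg.

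| First event | Table 4 | Section 5.1.2.1 text | Result |
|---|---|---|---|
| Grade 3 neuropathy | Stop permanently | Rule A: lower level; Rule B not yet met on recurrence | Conflict |
| Grade 3 AST/ALT elevation | Stop | As above | Conflict on the plain reading |
| Grade 3 other event | Stop | As above | Conflict on the plain reading |
| Grade 3 hyponatremia | Stopping optional | As above | Compatible |
| Grade 3–4 diarrhea, nausea, vomiting | Stepwise reduction, no stop line | Rules A and B; excepted from Rule C | Compatible |
| Grade 4 AST/ALT elevation, other event, hyponatremia | Stop | Rule C: stop | Agree |
| Grade 4 neuropathy | Stop at first occurrence | Reduced dose never reached | Not at issue |
| Interstitial lung disease | Stop once diagnosed, any grade | Not a recurrence question | Not at issue |

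**Count.** Table 4 has six event classes: gastrointestinal, neuropathy, hyponatremia, AST/ALT, interstitial lung disease and other. Three of six are affected, each in its Grade 3 row only.

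**Sensitivity to reading.** Rule A follows directly on the re-escalation allowance and ends by barring re-escalation a second time. It can therefore be read as covering only a subject who went back up and then had the event again. Take such a subject: reduced to 200 mg, re-escalated to 300 mg, recurrence at Grade 3.

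- *AST/ALT and other events.* If Table 4's condition refers to the dose at the time of recurrence, 300 mg is not a reduced dose. The stop line is not triggered and text and table agree.
- *Neuropathy.* Table 4 stops on any Grade 3 or higher recurrence after resuming, whatever the dose. Rule A says to reduce. They still conflict.

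Rule B can also be read as an outer limit: it says when stopping becomes mandatory and does not forbid stopping sooner. If both readings are adopted, the AST/ALT and other rows can be squared with the text. The neuropathy row cannot.

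**Scope difference.** Rule B is limited to study drug-related toxicity. The Table 4 rows state no such limit.

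**Synopsis.** It states Rule C without the exception for diarrhea, nausea and vomiting. For a Grade 4 event of that kind recurring at Grade 3 or higher, the synopsis stops drug, while Section 5.1.2.1 exempts the event and Table 4 allows a lower level.

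**The case against.** The best case for the plan is that general text gives way to a specific table. Rule B sets an outer limit, Rule A concerns recurrence after re-escalation, and a site that follows Table 4 breaches neither. The practical reach also looks small. In the early studies the only drug-related events leading to withdrawal of drug were nausea, vomiting and hyponatremia (Protocol Section 1.3.1), none of which is in a conflicting row. The investigator may already stop for unacceptable toxicity or in the subject's interest (Section 6.1). The primary analysis uses the FAS, and subjects who stop before progression continue to be imaged, subject to the limits in Section 5.3.

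Much of this stands. It softens the AST/ALT and other rows and keeps the matter away from the definition of the primary analysis. It does not clear neuropathy. Nor does the protocol state the precedence that the argument needs: a site would have to infer that a catch-all row for other events displaces the general rule printed above it.

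A reader might go further and infer that the text stops drug for Grade 3–4 toxicity only after two reductions, or that dose level -2 is both allowed and ruled out in general. The documents do not support either. The text also stops drug for persistence and, under Rule C, for most Grade 4 events that return at Grade 3 or higher. Level -2 remains reachable through gastrointestinal events, recurrent Grade 2 neuropathy, Grade 3 hyponatremia, or a different event arising at 200 mg. Table 4 also speaks of a reduced dose, which on its plain meaning includes the first but does not name it.

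**Conclusion.** The inconsistency is real and limited. For a first Grade 3 neuropathy, text and table give different instructions on Grade 3 or higher recurrence under either reading of Rule A. For Grade 3 AST/ALT elevation and other Grade 3 events they differ on the plain reading, and agree only if two interpretations that the protocol does not state are both adopted. Three of six event classes are affected, in Grade 3 rows only. For Grade 4 events, text and table are consistent within Section 5.1.2.1.

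Frequency cannot be stated. The four drug-related ALT-increase SAEs in Study 8273-CL-0101 show that the event class occurs, but they are not a count of Grade 3 recurrences on a reduced dose, and the documents give no such count. Effects on deviation classification, PPS membership and dose intensity are therefore possible consequences of unknown size. The documents do not support a claim that the primary result is compromised. The point is worth correcting because it concerns handling of a safety event in one arm and because correction is cheap.

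**What to change.** Reconcile the general paragraph of Section 5.1.2.1, Table 4 and the synopsis so that each event class and grade has one rule on recurrence. In the same change:

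- state which passage governs if text and table differ;
- say whether the sentence on reducing to the lower level applies only after re-escalation;
- say whether the Table 4 rows are limited to drug-related events, as the two-reduction sentence is;
- make the Grade 4 rule in the synopsis match Section 5.1.2.1 on diarrhea, nausea and vomiting.

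Which rule applies to each class is for the sponsor's medical team. Once it is settled, PD2, PD3 and the PPS dose criterion can be applied to one rule. The cost is wording in the next amendment and a clarification letter to sites. No sample size or analysis method changes.
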